5.5. Justification for Dose

Oral doses of 50, 100, and 200 mg lasmiditan are envisaged to be clinically effective doses for the target population, based on data obtained from previous completed studies.

6. Study Population

Eligibility of subjects for the study will be based on the results of screening medical history, physical examination, vital signs, clinical laboratory tests, and ECG.

The nature of any conditions present at the time of the physical examination and any preexisting conditions will be documented.

Screening may occur up to 28 days prior to enrollment. Subjects who are not enrolled within 28 days of screening may be subjected to an additional medical assessment and/or clinical measurements to confirm their eligibility.

Prospective approval of protocol deviations to recruitment and enrollment criteria, also known as protocol waivers or exemptions, are not permitted.

6.1. Inclusion Criteria

Subjects are eligible for inclusion in the study only if they meet all of the following criteria at screening and/or enrollment:

- [1] are overtly healthy Chinese (all 4 biological grandparents and both biological parents to be of Chinese origin) males or females, as determined by medical history and physical examination

- [1a] male subjects will not be subject to any specific contraception requirements

- [1b] women of childbearing potential must test negative for pregnancy at screening and on Day -1, and must agree to use 1 highly effective (<1% failure rate) method of contraception or 2 effective methods of contraception during the study and for 30 days following the last dose of IP.

Highly effective methods of contraception include oral contraceptives, implanted contraceptives, or intrauterine devices. Effective methods of contraception include male or female condoms with concomitant use of spermicide, diaphragm with spermicide, or cervical sponges. Barrier methods without the concomitant use of spermicide or the use of male and female condoms as a double-barrier method are not acceptable.

Women of childbearing potential who practice abstinence or are in same-sex relationships, as their preferred and usual lifestyle, must agree to either remain abstinent or stay in a same-sex relationship without sexual relationships with males. Periodic abstinence (e.g., calendar, ovulation, symptothermal, postovulation methods), declaration of abstinence for the purpose of the study, and withdrawal are not acceptable.

[1c] women of non-childbearing potential may participate and include those who are:

- infertile due to surgical sterilization (hysterectomy, bilateral oophorectomy, or tubal ligation), congenital anomaly such as Mullerian agenesis, or
- postmenopausal, defined as:
 - a woman of at least 50 years of age with an intact uterus, not on hormone therapy, who has had either cessation of menses for at least 1 year or at least 6 months of spontaneous amenorrhea with a follicle-stimulating hormone level >40 mIU/mL, or
 - a woman 55 years of age or older, not on hormone therapy, who has had at least 6 months of spontaneous amenorrhea, or
 - a woman of at least 55 years of age with a diagnosis of menopause prior to starting hormone-replacement therapy

[2] are aged between 18 and 65 years, inclusive, at screening

[3] have a body mass index (BMI) of 18.0 to 32.0 kg/m², inclusive

[4] have clinical laboratory test results within normal reference range for the population or investigative site, or results with acceptable deviations that are judged to be not clinically significant by the investigator

[5] have venous access sufficient to allow for blood sampling as per the protocol

[6] are reliable and willing to make themselves available for the duration of the study and are willing to follow study procedures

[7] are able and willing to give signed informed consent

6.2. Exclusion Criteria

Subjects will be excluded from study enrollment if they meet any of the following criteria at screening and/or enrollment:

[8] are investigative site personnel directly affiliated with this study and their immediate families. Immediate family is defined as a spouse, biological or legal guardian, child, or sibling

[9] are Lilly employees or are employees of third-party organizations involved with the study

[10] are currently enrolled in a clinical study involving an IP or any other type of medical research judged not to be scientifically or medically compatible with this study

[11] have participated, within the last 30 days, in a clinical study involving an IP. If the previous IP has a long half-life, 5 half-lives or 30 days (whichever is longer) should have passed

- [12] have previously completed or withdrawn from this study or any other study investigating lasmiditan, and have previously received the IP
- [13] have known allergies to lasmiditan, related compounds or any components of the formulation
- [14] have a history of, or ECG findings of, clinically significant bradycardia, heart block, tachyarrhythmia, bradyarrhythmia, or have any other abnormality that, in the opinion of the investigator, increases the risk of participating in the study
- [15] have an abnormal blood pressure and/or pulse rate as determined clinically significant by the investigator
- [16] have a significant history of or current cardiovascular, respiratory, hepatic, renal, gastrointestinal, endocrine, hematological, or neurological disorders capable of significantly altering the absorption, metabolism, or elimination of drugs; of constituting a risk when taking the IP; or of interfering with the interpretation of data. Examples of excluded conditions include, but are not limited to; hypertension, angina, heart failure, asthma (childhood asthma is acceptable), chronic obstructive airways disease, hepatitis, cirrhosis, renal impairment, diabetes, anemia, migraine, fits, seizures (except febrile convulsions), significant head trauma, surgical resection of bowel (appendectomy is acceptable), or any other condition requiring chronic medication
- [17] have a history of, show evidence of, or are undergoing treatment for significant active neuropsychiatric disease (for example, manic depressive illness, schizophrenia, depression)
- [18] have a recent history of a suicide attempt (30 days within screening visit and any time between screening visit and baseline), evidence of suicide-related thought or behavior as identified by the C-SSRS, or are clinically judged by the investigator to be at risk for suicide
- [19] have a history of central nervous system (CNS) conditions such as strokes, transient ischemic attack, significant head trauma, CNS infections, migraines, brain surgery, or any other neurological conditions that, in the opinion of the investigator, increases the risk of participating in the study
- [20] regularly use known drugs of abuse and/or show positive findings on drug screening
- [21] show evidence of human immunodeficiency virus (HIV) infection and/or positive human HIV antibodies
- [22] show evidence of hepatitis C and/or positive hepatitis C antibody
- [23] show evidence of hepatitis B and/or positive hepatitis B surface antigen
- [24] are women with a positive pregnancy test or women who are lactating

- [25] have used or intend to use over-the-counter or prescription medication including herbal medications and Chinese traditional medicine within 14 days prior to admission to the CRU and until discharge from the study (with the exception of hormone-replacement therapy, oral contraceptives, or occasional acetaminophen use)
- [26] have donated blood of more than 400 mL within 1 month prior to screening
- [27] have an average weekly alcohol intake that exceeds 21 units per week (males) and 14 units per week (females), or are unwilling to stop alcohol consumption 48 hours prior to admission and throughout the duration of the study (1 unit = 12 oz or 360 mL of beer; 5 oz or 150 mL of wine; 1.5 oz or 45 mL of distilled spirits)
- [28] currently use or have a history of drug or alcohol abuse
- [29] are smokers of more than 10 cigarettes or e-cigarettes, or 3 cigars or 3 pipes per day, and are unable to refrain from smoking for 48 hours prior to admission to and while resident at the CRU
- [30] in the opinion of the investigator or sponsor, are unsuitable for inclusion in the study

6.2.1. Rationale for Exclusion of Certain Study Candidates

Criteria [1] to [7] define a healthy population that is suitable for evaluation in a Phase 1 study and define the Chinese population for the purposes of this study. The use of lasmiditan in Chinese patients is anticipated, thus this study will specifically examine the PK, safety, and tolerability in Chinese subjects.

Criteria [8] and [9] prevent conflict of interest in study participants. Criteria [10] to [30] predominantly exclude medical conditions, medical intolerances, and concomitant medications that may confound the assessment of study endpoints, or may affect subject or investigative site safety.

6.3. Lifestyle and/or Dietary Requirements

Throughout the study, subjects may undergo medical assessments and review of compliance with requirements before continuing in the study.

6.3.1. Meals and Dietary Restrictions

Lasmiditan will be administered after an overnight fast of at least 8 hours. Subjects will remain fasting for 3 hours postdose on Days 1 and 10. On Days 2 to 9, a light breakfast will be allowed 1 hour postdose. With the exception of water given with the lasmiditan dose, subjects will abstain from fluid intake for 1 hour before and for 1 hour after dosing.

Standardized meals will be provided at all other times while resident at the CRU.

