Up to 36 subjects (12 subjects per cohort) may be enrolled and randomized so that approximately 8 subjects per cohort, who receive lasmiditan, complete the study.

Statistical Analysis:

Safety parameters that will be assessed include safety lab parameters and vital signs. The parameters will be listed and summarized using descriptive statistics as appropriate.

Pharmacokinetic parameter estimates for lasmiditan and metabolites M7, M8, (S,R)-M18, and (S,S)-M18 will be calculated by standard noncompartmental methods of analysis. Trough concentrations of lasmiditan and its metabolites will be evaluated graphically and/or descriptively for achievement of steady-state.

Log-transformed C_{\max} and AUC parameters (AUC[0- ∞] for Day 1 and AUC[0- τ] for Day 10) will be evaluated using a power model (where the log of the dose will be an explanatory variable) to estimate ratios of dose-normalized geometric means and the corresponding 90% confidence intervals (CIs). The estimated ratio between the highest and lowest doses will be used to assess dose proportionality. The intersubject coefficient of variation will be derived.

2. Schedule of Activities

Study Schedule Protocol H8H-MC-LAIC

Procedure	Screening	Day									FU/ ED	Comments	
	D-28 to D-2	-1	1	2	3	4	5 to 9	10	11	12			
Informed Consent	X												
Subject Admission to CRU		X											
Subject Discharge from CRU										X			
Lasmiditan or Placebo Administration			X			X	X	X					Approximately 72 hours between the first (D1) and second (D4) lasmiditan/placebo doses.
Medical History	X												
Urine Drug Screen	X	X											
Alcohol test	X	X											
Height	X												
Weight	X	X									X		
Single Vital Signs (supine)	X		P, 0.5, 1, 2, 2.5, 3, 4, 6, 8, 12 h	24 h		P, 0.5, 1, 2, 2.5, 3, 4, 6, 8, 12 h	24 h (D5)	P, 0.5, 1, 2, 2.5, 3, 4, 6, 8, 12 h	24 h		X		Time points relative to dosing on D1, D4, and D10. Vital signs may be performed at other times as clinically indicated, determined by the investigator.
Single Orthostatic Vital Signs	X		P, 2 h	24 h		P, 2 h	24 h (D5)	P, 2 h	24 h				Time points relative to dosing on D1, D4, and D10. Vital signs may be performed at other times as clinically indicated, determined by the investigator.
Clinical Laboratory Tests	X	X	P			P		P		X	X		See Appendix 2 , Clinical Laboratory Tests, for details.

Procedure	Screening	Day										FU/ ED	Comments	
		-1	1	2	3	4	5 to 9	10	11	12				
	D-28 to D-2													FU approximately 7 to 10 days post final dose.

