3.3. Benefit/Risk Assessment

Oral doses of lasmiditan up to the highest single and multiple oral dose given (400 mg) were well tolerated in healthy subjects, with no drug-related serious adverse events (SAEs) or withdrawals due to AEs as of 05 March 2018. Lasmiditan caused no significant QT prolongation either at 100 or 400 mg, and no clinically significant changes in clinical laboratory data. Lasmiditan has been associated with transient lowering of heart rate (on average about 8 to 12 bpm). Throughout this study, vital signs will be closely monitored for effects of lasmiditan on heart rate. Although nervous system disorders were commonly reported as AEs, especially at higher dose levels, they were generally mild or moderate in intensity. Dosing of subjects in this study will be conducted in an inpatient setting, and subjects will be monitored in-house for at least 48 hours after the last dose of investigational product (IP).

There is no anticipated therapeutic benefit for the subjects.

More information about the known and expected benefits, risks, SAEs, and reasonably anticipated AEs of lasmiditan are to be found in the IB.

4. Objectives and Endpoints

Table LAIC.1 shows the objectives and endpoints of the study.

Table LAIC.1. Objectives and Endpoints

Objectives	Endpoints

Primary To evaluate the PK of single and multiple doses of lasmiditan in healthy Chinese subjects.
	AUC(0-∞) [single-dose only], AUC(0-τ), C _{max} , and t _{max} .

Secondary To explore the safety and tolerability of single and multiple oral doses of lasmiditan in healthy Chinese subjects.
	Incidence of SAEs and TEAEs.

Exploratory To evaluate the PK of metabolites M7, M8, (S,R)-M18, and (S,S)-M18 in healthy Chinese subjects.
	AUC(0-∞), C _{max} , and t _{max} .

Abbreviations: AUC(0-∞) = area under the concentration versus time curve from time zero extrapolated to infinity; AUC(0-τ) = area under the concentration versus time curve over a dosing interval; C_{max} = maximum observed plasma concentration; PK = pharmacokinetics; SAE = serious adverse event; TEAE = treatment-emergent adverse event; t_{max} = time of maximum observed plasma concentration.

5. Study Design

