#### **9.4.4 Vital signs**

Orthostatic vital signs will be calculated as the standing value, minus the last supine value taken prior to the standing value.

Vital signs data will be summarized by treatment and timepoint together with changes from baseline, where baseline is defined as Day 1, predose. Figures of mean vital signs and mean changes from baseline profiles by treatment will be presented.

Furthermore, values for individual subjects will be listed.

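### SAP 9.4.4 measures Day 4 and Day 10 vital-sign changes only from Day 1 predose, so each arm's change mixes the acute dose effect with between-day drift; the Day 4 profile also has a different meal condition.

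*Protocol*

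**What the plan says.** **Readings.** The Schedule of Activities (Protocol Section 2) sets the same supine vital-sign profile on Days 1, 4 and 10: "P, 0.5, 1, 2, 2.5, 3, 4, 6, 8, 12 h". Orthostatic readings on those days are at predose and 2 h. Each profile is timed from that day's dose, so each of the three days has its own predose value.

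**Baseline.** SAP 9.4.4 states: "Vital signs data will be summarized by treatment and timepoint together with changes from baseline, where baseline is defined as Day 1, predose". It also plans figures of mean values and mean changes by treatment. It specifies neither a change from same-day predose nor a lasmiditan-minus-placebo change.

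**Meals.** Protocol 6.3.1 states: "Subjects will remain fasting for 3 hours postdose on Days 1 and 10". The next sentence reads: "On Days 2 to 9, a light breakfast will be allowed 1 hour postdose". Day 4 falls under the second rule. For the rest of the stay, "Standardized meals will be provided at all other times while resident at the CRU".

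**Placebo.** Each cohort has 10 lasmiditan and 2 placebo subjects (Protocol 5.1). Placebo is pooled across cohorts (SAP Section 8) and shown as its own treatment group (SAP Section 6).

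**The concern.** The secondary objective covers safety after single and multiple doses. Protocol 3.3 names a transient fall in heart rate, about 8 to 12 bpm on average, and undertakes to watch vital signs closely for it. SAP 9.4.5 says ECGs will not be reported, so the vital-sign tables and figures are the only planned summary of heart rate.

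In those tables, a Day 10 change within a lasmiditan arm is the acute effect of the Day 10 dose plus whatever has shifted over the 9 days since baseline. A Day 4 change carries 3 days of shift and, after 1 h, a possible breakfast effect. If an arm's curve is smaller on a later day, a reader could take it for tolerance when the drug effect has not changed. A larger one could be taken for accumulation.

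**Working it through.** The documents give no power figure and no variability for vital signs, so there is no figure of the plan's own to reproduce beyond the head count: 3 × (10 + 2) = 36 subjects, with 3 × 2 = 6 on placebo.

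**1. Where the meal rules differ.** Readings up to 1 h are fasted on all three days. From 1 h to 3 h, Days 1 and 10 are fasted and Day 4 need not be. The supine readings affected are those at 2, 2.5 and 3 h, close to the median tmax of 1.5 to 2.5 h (Protocol 3.2). The only same-day postdose orthostatic reading on Day 4, at 2 h, is also affected. Day 4 has only a predose PK sample, so a difference in exposure could not be checked.

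**2. Is same-day predose a usable reference?** With the stated half-life of about 4 h, the parent drug left 24 h after a dose is 2^-(24/4) = 2^-6 = 1.6%. Before Day 4 the gap is at least 72 h, or 72/4 = 18 half-lives. For the parent drug, predose on both days is close to drug-free. Some metabolites last longer (up to about 21 h), but Protocol 3.2 describes them as generally inactive.

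**3. What the planned output can recover.** With complete data,

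(mean change at Day k, time t, from Day 1 predose) − (mean change at Day k predose from Day 1 predose) = mean same-day change at t.

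So the planned predose changes show the drift, and subtraction gives the same-day mean. It does not give the SD of the same-day change.

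**4. Illustration of the reading problem (all values assumed).** Drug effect −10 bpm at 2 h, Day 4 meal effect +5, drift +2 on Day 4 and +4 on Day 10.

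| 2 h heart-rate change, bpm | Day 1 | Day 4 | Day 10 |
|---|---|---|---|
| Lasmiditan arm, from Day 1 predose | −10 | −10 + 5 + 2 = −3 | −10 + 4 = −6 |
| Lasmiditan arm, from same-day predose | −10 | −10 + 5 = −5 | −10 |
| Lasmiditan minus placebo, either baseline | −10 | −10 | −10 |

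A simulation with these values gave the same means. The same-day baseline corrects Day 10 but leaves the meal effect in the Day 4 arm mean. The placebo contrast removes both, provided they are common to the arms.

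**5. Precision (SDs assumed).** Let the between-day SD within a subject be s_d = 3 to 6 bpm and the within-day SD be s_e = 4 bpm.

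- SD of change from Day 1 predose = √(2·s_d² + 2·s_e²): √(18 + 32) = 7.1 at s_d = 3; √(72 + 32) = 10.2 at s_d = 6.
- SD of change from same-day predose = √(2·s_e²) = √32 = 5.7, which is 20% to 45% smaller.
- Standard error of a 10 v 6 contrast = SD × √(1/10 + 1/6) = SD × 0.516: 3.7 to 5.3 bpm with the Day 1 baseline, 2.9 bpm with the same-day baseline.
- 95% half-width (t on 14 df = 2.145): 7.8 to 11.3 bpm against 6.3 bpm.

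The cited effect is 8 to 12 bpm.

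**The case against.** A reader might infer that all three profiles are taken under different meal conditions, and that the design therefore cannot separate the acute effect from meals and drift. The documents do not support that.

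- Days 1 and 10 share one meal rule. Day 10, the seventh consecutive daily dose, is the repeated-dose profile. Day 4 is close to a second first dose for the parent drug. The single-dose v repeated-dose comparison has no planned meal mismatch up to 3 h.
- A randomized placebo group follows the same meal and stay rules and is summarised at the same timepoints. Protocol 5.4 gives limiting bias in the safety objective as the reason for that design.
- Drift is visible in the planned predose changes, and individual values are listed.
- The limits on caffeine, alcohol, smoking and exercise start 48 h before admission. They already apply at Day 1 predose and are weak candidates for later drift.
- Orthostatic values are standing minus supine, so a shift common to both postures cancels.
- Vital signs are descriptive, no safety inference is planned, and the listed secondary endpoint is incidence of SAEs and TEAEs.
- Day 1 predose is the only baseline before any treatment, so it has a proper use.

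All of this stands. It shows that the data can answer the question. The remaining gap is in the analysis: the comparison with placebo rests on about 6 subjects, no placebo-adjusted or same-day change is specified, and the baseline chosen for Days 4 and 10 adds between-day variance to every change. Subtracting reported means does not recover the SD of the same-day change.

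**Conclusion.** The point holds as an analysis gap of low severity, together with a comparability flaw confined to Day 4 after 1 h. The design is not one that cannot answer its question. The planned tables and figures allow drift and meal effects to be separated from the acute effect only indirectly and with less precision than the collected data permit.

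Under the assumed SDs, a same-day baseline cuts the standard error of the 10 v 6 contrast from 3.7–5.3 to 2.9 bpm. The gain shrinks towards zero as the between-day SD does. The meal and drift sizes in the illustration are also assumptions; the documents give no values for any of them. The differing meal rules, the single baseline, and the absence of a same-day or placebo-adjusted change come directly from the text.

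**What to change.** 1. **SAP 9.4.4.** For Days 4 and 10, also summarise and plot change from same-day predose for supine and orthostatic vital signs, with the pooled placebo group alongside. Keep change from Day 1 predose to show cumulative change, including any effect that persists to the next predose reading. Cost: one more derived variable and its tables and figures, from data already scheduled for collection.
2. **Day 4 meals.** The same-day baseline does not remove a meal effect within an arm. Reconcile the Day 4 meal condition in Protocol 6.3.1 with the other two profile days, or state the difference wherever Day 4 is compared with Day 1 or Day 10. Cost: a wording change or a footnote.
3. **Wording.** The breakfast rule refers to a time after dosing on Days 2 to 9, but the Schedule of Activities has no dose on Days 2 and 3. Reconcile the two. Cost: one sentence.

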6.3.2. Caffeine, Alcohol, and Tobacco

Subjects will refrain from consuming xanthine- or caffeine-containing food and drinks from 48 hours prior to admission to the CRU until the end of the study period.

Subjects will refrain from consuming grapefruit and grapefruit-containing products from 7 days prior to admission to the CRU until discharge from the study.

Alcohol consumption is not permitted for 48 hours prior to admission to the CRU and for the duration of the study.

Subjects will refrain from smoking for 48 hours prior to admission to and while resident at the CRU.

6.3.3. Activity

No strenuous exercise is permitted for 48 hours prior to admission to the CRU until discharge from the study.

6.4. Screen Failures

Individuals who do not meet the criteria for participation in this study (screen failure) may not be re-screened.

7. Treatment

7.1. Treatment Administered

This study involves a comparison of single (Day 1) and repeated (Days 4 to 10) doses of 50, 100, and 200 mg lasmiditan administered orally, with placebo.

Table LAIC.2 shows the treatment regimens at for each cohort.

Table LAIC.2. Treatments Administered

Cohort	Dose level	Number of tablets administered per dose
1	50 mg lasmiditan or placebo	1 x 50-mg tablet
2	100 mg lasmiditan or placebo	1 x 100-mg tablet
3	200 mg lasmiditan or placebo	2 x 100-mg tablet

Tablets of lasmiditan or placebo will be orally administered with approximately 240 mL of room-temperature water in the morning of each dosing day, in a sitting position. Subjects will not be allowed to lie supine for 2 hours after dosing, unless clinically indicated or for study procedures.

The investigator or designee is responsible for:

- explaining the correct use of the IP(s) to the site personnel
- verifying that instructions are followed properly
- maintaining accurate records of IP dispensing and collection
- and returning all unused medication to Lilly or its designee at the end of the study

Note: In some cases, sites may destroy the material if, during the investigative site selection, the evaluator has verified and documented that the site has appropriate facilities and written procedures to dispose of clinical materials.

